Injection-site assessment for erythema, induration, pruritus, and edema (hour)			0, 0.25	X		X		X								Times with respect to start of dosing. Zero-hour assessments within 1 minute following injection. Time allowance for 0.25-hour assessment is ±5 minutes. Additional assessments performed if deemed necessary by the investigator.	
Injection-site bleeding assessment (hour)			0													Time with respect to start of dosing. Zero-hour assessment within 1 minute following injection.	

Procedure	Screening ≤28 days	Days														Comments
		-1	1	2	4 ±1d	8 ±1d	11 ±1d	15 ±2d	22 ±2d	29 ±2d	43 ±2d	57 ±3d	71 ±3d	85/ED ±3d		
Pain assessment (VAS) (minutes)		1, 5, 15, 30, 60, 120														Time with respect to start of dosing. Time points are minutes post-injection as follows: within 1 minute of the end of injection, 5 (±1.5), 15 (±2), 30 (±2), 60 (±5), 120 (±5) minutes
LY3074828 pharmacokinetic sampling (hour)		0, 2, 6	24	X	X	X	X	X	X	X	X	X	X	X	X	Times with respect to start of dosing. Zero-hour collection immediately (within 15 minutes) before dosing. Time allowance for 2-, 6-, and 24-hour time points: ±15, ±30, and ±90 minutes, respectively. For the 2-hour postdose timepoint, VAS pain assessment should be conducted prior to PK sample collection.
Immunogenicity sample		Predose					X		X		X		X		X	LY3074828 antibody sample. In the event of an AE that could be immunologically mediated, additional samples may be taken (See Section 9.6.1). Predose sample may be collected within 2 hours prior to planned dosing.
Pharmacogenetics sample			X													

Abbreviations: AE = adverse event; AI = autoinjector; BMI = body mass index; CRU = clinical research unit; d = day; ECG = electrocardiogram; ED = early discontinuation; FSH = follicle-stimulating hormone; ICF = informed consent form; PFS = pre-filled syringe; TB = tuberculosis; VAS = visual analog scale.

Site should schedule activities as appropriate. For the 2-hour postdose timepoint, VAS pain assessment should be conducted prior to pharmacokinetic sample collection. In other cases where several study procedures are scheduled at the same time, follow this order of priority for procedures: pharmacokinetic samples, clinical laboratory tests, immunogenicity sample, stored sample, ECG, vital signs, pain assessment, injection-site assessment, such that pharmacokinetic sample collection occurs as close to the nominal collection time as possible.

3. Introduction

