No deaths, serious adverse events (SAEs), or discontinuations due to an adverse event (AE) have been reported in any of the Phase 1 studies.

In the completed Study AMAA, a total of 82 treatment-emergent AEs (TEAEs) were reported by 37 subjects. The most commonly reported TEAEs in this study were nasopharyngitis and headache. There were no drug-related TEAEs of National Cancer Institute Common Terminology Criteria for Adverse Events Grade 2 or higher reported in Study AMAA.

In the completed Study AMAE, the incidence of TEAEs was similar between the 125 mg LY3074828 lyophilized formulation and the 125 mg LY3074828 PFS solution formulation, with a notably higher number of TEAEs reported by healthy subjects who received 500 mg LY3074828 solution formulation. The most common TEAEs related to study treatment were events occurring at the site of injection, including injection-site reaction (ISR) and injection-site hemorrhage. Across all formulations, the majority of TEAEs reported during the study were mild, with only 1 TEAE that was moderate in severity but not related to study drug.

There were no obvious trends in the pattern of AEs across studies apart from ISRs. Injection-site pain, of short duration (usually hours), has been reported in both the completed and ongoing clinical pharmacology studies. Preliminary data from Studies AMAE and AMAL showed that most ISRs were mild or moderate in severity, with severe injection-site pain reported in 2% of ISRs in the 125-mg SC solution test formulation group.

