3.3. Benefit/Risk Assessment

Based on LY3074828 nonclinical and preliminary clinical data, there are no anticipated risks requiring monitoring beyond those for a typical humanized monoclonal antibody in human studies. As with other immunomodulatory therapies, LY3074828 may increase the risk of developing an infection or may exacerbate an existing serious infection. These may include opportunistic infections and reactivation of latent infections, such as tuberculosis (TB) and hepatitis B. Subjects will therefore be screened for hepatitis B/C, human immunodeficiency virus (HIV), and TB. Immunomodulatory therapies may increase the risk of malignancies; however, due to only single doses of LY3074828 being administered in this study, it is not considered necessary to monitor for such effects.

Based on available data from Studies AMAA and AMAD, TE-ADAs have been observed in 2 of the 11 healthy subjects that received SC doses of LY3074828; however, titers were \leq 1:160. In the 33 patients with psoriasis who received single IV doses of LY3074828, TE-ADAs were detected in 3 subjects (Study AMAA).

No clinically significant safety or tolerability concerns have been identified in patients or healthy subjects to date for LY3074828 up to the highest doses given (single 2400-mg IV doses and 2400-mg SC doses).

Healthy subjects are not expected to derive any benefit from participating in studies with administration of LY3074828.

As this study will use PFS and AIs, device-based risks will be evaluated. Possible device-based risks include local effects such as pain at the injection sites from either the needle or the solution entry into the SC tissue, swelling, erythema, bleeding, and bruising. These risks are mitigated by training of investigative site staff on proper injection techniques. Systemic effects may include sweating, feeling faint, or fever, as a sign of infection.

More information about the known and expected benefits, risks, SAEs, and reasonably anticipated AEs of LY3074828 are found in the compound IB, and risks as well as reasonably anticipated adverse device effects of the AI are found in the device IB.

4. Objectives and Endpoints

Table AMBE.1 shows the objectives and endpoints of the study.

Table AMBE.1. Objectives and Endpoints

Objectives	Endpoints

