9.4.4.3. Injection-Site Assessments

Injection site findings (including erythema, induration, pruritus, and edema) will be captured on a separate ISR form, as indicated in the Schedule of Activities (Section 2).

Data from injection site evaluations (including pain) which are recorded as a result of specific questionnaire/s will not be reported as AEs. If the investigator determines that the ISR is clinically significant or if it is an unsolicited event (volunteered by subject), the event will be captured in the subject's eCRF as an AE.

If an ISR is deemed to be an AE, the ISR form will be used to capture specific information about this reaction (eg, degree and area of erythema).

Injection-site tenderness on contact reported by subjects may be recorded as an AE, but is not required to be captured in ISR form.

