9.4.4.4. Bleeding Assessment

All injection sites will be observed at the times indicated in the Schedule of Activities (Section 2) by the investigator or designee, and the presence of visible bleeding will be recorded on the eCRF. A bandage may be placed on the injection site after assessment.

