10.3.1.2. Statistical Evaluation of Safety

10.3.1.2.1. *Injection-Site Pain*

The intensity of pain at the injection site within 1 minute of the end of injection and 5 minutes after the end of the injection will be evaluated, as reported by the subject and measured according to the 0- to 100-mm VAS. VAS scores will be categorized into mild (0- to 30-mm), moderate (31- to 70-mm), and severe (71- to 100-mm). Assessments will also be performed at 15, 30, 60, and 120 minutes post-injection; however, the primary endpoints will be the 1- and 5-minute assessments.

Descriptive statistics will be used to summarize the intensity of pain at each time point.

A linear fixed-effects model will be used to analyze the 1- and 5-minute post-injection pain VAS scores separately. The model will include device and injection location as fixed effects. The least squares (LS) means and differences in LS means will be presented along with the corresponding 90% CI overall and by location as subgroups. The distribution of the data will be explored prior to analysis to determine whether data transformation is required. It is possible that the pain scores will be 0, so if the distribution of the data implies that a log-transformation is required then the score may be updated to $\log(VAS+1)$ to allow for the inclusion of the 0 values in the analysis. If the assumptions of this model appear violated, a non-parametric method may be used.

10.3.1.2.2. *Duration of Injection*

The duration of the injection (measured in seconds) will be summarized for each drug delivery device for each injection site.

10.3.1.2.3. *Injection-Site Assessments*

The incidence of the following AEs will be listed and summarized for each drug delivery device for each injection site: erythema, induration, pruritus, and edema. Occurrence of bleeding will be listed.

10.3.1.2.4. *Statistical Evaluation of Other Safety Parameters*

Other safety parameters that will be assessed include clinical laboratory parameters and vital signs. The parameters and changes from baseline (predose), where appropriate, will be listed and summarized using standard descriptive statistics. Additional analyses will be performed if warranted upon review of the data.

10.3.2. *Pharmacokinetic Analyses*

10.3.2.1. *Pharmacokinetic Parameter Estimation*

Pharmacokinetic parameter estimates for LY3074828 will be calculated by standard noncompartmental methods of analysis.

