9.4.7 Injection-Site Reactions

Injection-site reactions will be evaluated through the collection of pain assessments and specific site assessments for local tolerability, which will evaluate erythema, induration, pruritus, and edema. Data from injection-site evaluations (including pain), which are recorded as a result of specific questionnaires, will not be reported as AEs. However, injection site reactions may be reported as AEs if:

- a) Spontaneously reported by a subject.
- b) At the discretion of the principal investigator.

Injection-site reaction data will be listed and reactions reported as AEs will be summarized by treatment in frequency tables.

Any bruising or bleeding from the injection site will also be listed.

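### Bruising is a named device risk that the SAP promises to list, but no scheduled assessment names it, so later bruising reaches the data only through non-systematic AE reporting

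*SAP*

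**What the plan says.** Protocol 3.3 states that device-based risks will be evaluated. The possible local effects it names, besides pain, are "swelling, erythema, bleeding, and bruising". Protocol 3.2 gives the history: in Study AMAE the most common treatment-related TEAEs were events at the injection site, "including injection-site reaction (ISR) and injection-site hemorrhage".

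The Schedule of Activities (protocol Section 2) has two relevant rows:

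- The injection-site assessment is done at 0 h and 0.25 h on Day 1 and again on Days 2, 8 and 15. It names four signs: erythema, induration, pruritus and edema.
- The bleeding assessment is done once: "Zero-hour assessment within 1 minute following injection".

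Protocol 9.4.4.3 describes the record for the first: "Injection site findings (including erythema, induration, pruritus, and edema) will be captured on a separate ISR form". Protocol 9.4.4.4 describes the second: "the presence of visible bleeding will be recorded on the eCRF".

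On analysis, protocol 10.3.1.2.3 covers the four signs and adds "Occurrence of bleeding will be listed". It does not mention bruising. SAP 9.4.7 widens this: "Any bruising or bleeding from the injection site will also be listed". Both protocol 9.4.4.3 and SAP 9.4.7 say that findings solicited by questionnaire are not AEs. A reaction becomes an AE if the subject volunteers it or on the investigator's judgement.

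**The concern.** The SAP promises an output for which neither document specifies a systematic data source. Staff inspect a marked injection site on three days after dosing, yet no named item asks whether it is bruised.

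This matters because the study is meant to bridge PFS administration to the AI (protocol 3.1), so local tolerability by device is part of what readers will look for. The study is open-label, and protocol 5.4 says that subjects and site staff will know the treatment. Whether a bruise is mentioned, or thought worth reporting, is then decided by people who know which device was used. Bruises reported as AEs can also enter the TEAE tables by treatment (SAP 9.4.1 and 9.4.7), while unreported ones leave no trace. A subject absent from the listing may have had no bruise or an unrecorded one, and the listing cannot tell the two apart.

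**Working it through.** The plan states no figure on this point, so the check is a cross-reading of the documents and a count.

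**1. Scheduled looks per sign (Schedule of Activities).**

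| Sign | Day 1 | Later days | Total |
|---|---|---|---|
| Erythema, induration, pruritus, edema | 2 (0 h, 0.25 h) | 3 (Days 2, 8, 15) | 2 + 3 = 5 each |
| Visible bleeding | 1 (0 h, within 1 minute) | 0 | 1 |
| Bruising | 0 named | 0 named | 0 |

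The later days are read from a table whose columns are imperfectly preserved. The zero for bruising does not depend on them.

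**2. Follow one case through the plan.** A subject has a bruise at the marked site on Day 2 and does not complain of it. The scheduled assessment asks for four other signs. The bleeding check was completed on Day 1. The bruise can still enter the data by one of these routes:

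- the subject volunteers it at an AE review (protocol 9.4.4.3, SAP 9.4.7);
- the investigator judges it clinically significant, or reports it at his or her discretion (same sections);
- the person completing the ISR form adds it of their own accord, since the wording of 9.4.4.3 is open-ended.

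None of these requires presence or absence to be recorded for every subject.

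**3. What one record is worth.** Protocol 5.2 randomizes 11 subjects to each of 6 arms, so each device has 3 × 11 = 33.

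- One bruise recorded or missed in a device-by-site arm: 1/11 = 9.1 percentage points.
- One bruise recorded or missed for a device: 1/33 = 3.0 percentage points.

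This is a sensitivity, not an estimate of how many would be missed. The documents give no rate for bruising or for injection-site hemorrhage.

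**The case against.** The strongest reply is that the plan already has several ways to catch a bruise. AE review is scheduled at every visit. Symptom-directed examinations follow dosing. Extra site assessments are allowed if the investigator thinks them necessary. Injection-site reactions are AEs of special interest with details required on the eCRF (protocol 9.2.1.2), and adverse device effects are reported separately (9.2.1.1). AE reporting evidently did detect injection-site hemorrhage in Study AMAE. SAP 9.1 lists all databased data, so any recorded bruise will appear. Bruising is not an endpoint, and only a listing is planned.

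Much of this stands, and it rules out four stronger readings:

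- A reader might infer that later bruising is picked up only by spontaneous report. It is not: protocol 9.4.4.3 and SAP 9.4.7 both give the investigator's judgement as a second route.
- A reader might infer that the ISR form has no place for bruising. The form is not among the documents, and 9.4.4.3 is worded inclusively, so a field cannot be ruled out.
- A reader might infer that the 1-minute bleeding check is mistimed. Protocol 9.4.4.4 defines it as a check for visible bleeding, and it should not be judged as a check for bruises.
- A reader might infer a false AI–PFS difference of some particular size or direction. The documents give neither a bruising rate nor any evidence on reporting by device.

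What the reply does not supply is a route that is the same for every subject. Investigator discretion is a second unstandardized filter, applied with knowledge of the device. The AMAE experience shows that some events were reported, not that all were. The details required for injection-site reactions need not cover bruising: protocol 3.2 names hemorrhage beside ISR as a separate event, and neither document says that a bruise counts as an ISR.

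**Conclusion.** The point holds in a limited form. A device risk named in the protocol, with a listing promised in the SAP, has no scheduled assessment that names it: zero looks, against five for each of the four listed signs. Later bruising is captured only through non-systematic AE reporting in an open-label device comparison. The resulting listing cannot be taken as complete or used for a fair comparison of AI with PFS.

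The consequence is confined to the description of local device tolerability, including any bruises that pass into the TEAE tables. The primary PK parameters and the VAS pain analysis are unaffected. The number of events missed cannot be calculated.

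The conclusion assumes that the unseen ISR form and eCRF follow the four signs named in the documents. If the form already has a required bruising field, what remains is to name it in the protocol and SAP.

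**What to change.** Add bruising (present/absent, largest diameter) to the existing injection-site assessment at 0.25 h and Days 2, 8 and 15. Make the change in the Schedule of Activities, in protocol 9.4.4.3 and on the ISR form, unless the form already has the field. In SAP 9.4.7, give the frequency of bruising by device and injection site. Take it from that form rather than from AE data, because solicited findings are not AEs.

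If the protocol and form are not to be changed, the minimum is one sentence in SAP 9.4.7 saying that the bruising listing draws on AE data only and is not systematically collected.

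The full change costs one item on an inspection already done at visits already scheduled, with minor protocol, form and SAP edits and no new visit or procedure. The downside is that slightly more minor findings will be recorded. Solicited bruises would still not count as AEs under protocol 9.4.4.3 unless volunteered or judged clinically significant, so the bruising table and the AE tables will show different counts, and a footnote should say so.

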9.4.8 Injection Duration

The duration of the injection (measured in seconds) will be summarized by treatment and listed.

9.4.9 Immunogenicity

Immunogenicity data will be listed and frequency tables will be presented. The frequency of treatment-emergent ADAs will also be calculated. Treatment-emergent ADAs are those that are induced or boosted by exposure to study drug, with a 4-fold increase in titer compared to baseline if ADAs were detected at baseline or a titer 2-fold greater than the minimum required dilution (1:10) if no ADAs were detected at baseline.

If a neutralization assay is performed, the frequency of neutralizing antibodies will be determined. The relationship between the presence (or absence) of antibodies and clinical parameters (AEs) will be assessed. Likewise, the relationship between the presence of antibodies and the PK parameters or concentrations of LY3074828 may be assessed if deemed appropriate.

9.4.10 Hepatic Monitoring

If a study subject experiences elevated alanine aminotransferase (ALT) $\geq 3 \times$ upper limit of normal (ULN), alkaline phosphatase (ALP) $\geq 2 \times$ ULN, or elevated total bilirubin (TBL) $\geq 2 \times$ ULN, liver tests should be repeated within 3 to 5 days including ALT, aspartate aminotransferase, ALP, TBL, direct bilirubin, gamma-glutamyl transferase, and creatine phosphokinase to confirm the abnormality and to determine if it is increasing or decreasing. Monitoring should continue until levels normalize and/or are returning to approximate baseline levels.

Additional safety data may be collected if required, as defined in the protocol. Where applicable, the following will be presented.

The subjects' liver disease history and associated person liver disease history data will be listed. Any concomitant medication of acetaminophen/paracetamol will be listed. Results from a magnetic resonance elastography scan and biopsy assessment will be listed, if performed.

Hepatic risk factor assessment data will be listed. Liver related signs and symptoms data will be summarized by treatment and listed. Alcohol and recreational drug use data will also be listed.

All hepatic chemistry, hematology, coagulation, and serology data will be listed. Values outside the reference ranges will be flagged on the individual subject data listings.

9.4.11 Other assessments

All other safety assessments not detailed in this section will be listed but not summarized or statistically analysed.

10. INTERIM ANALYSES

No formal interim analysis will be conducted. However, data may be accessed and analyzed while the trial is ongoing, but no changes to the study design are planned. An assessment committee will not be formed.

Available safety data will be reviewed at approximately Day 30 of the last cohort dosed in order to review emerging safety and tolerability data.

11. CHANGES FROM THE PROTOCOL SPECIFIED STATISTICAL ANALYSES

There were no changes from the protocol specified statistical analyses.

13. DATA PRESENTATION

13.1 Derived Parameters

Individual derived parameters (e.g. PK parameters) and appropriate summary statistics will be reported to three significant figures. Observed concentration data, e.g. C_{max} , should be reported as received. Observed time data, e.g. t_{max} , should be reported as received. N and percentage values should be reported as whole numbers. Median values should be treated as an observed parameter and reported to the same number of decimal places as minimum and maximum values.

13.2 Missing Data

Missing data will not be displayed in listings.

13.3 Insufficient Data for Presentation

Some of the TFLs may not have sufficient numbers of subjects or data for presentation. If this occurs, the blank TFL shell will be presented with a message printed in the centre of the table, such as, "No serious adverse events occurred for this study."

Leo Document ID = 3e3784ea-070a-42f6-aaa2-02560cd023fe

Approver: PPD

Approval Date & Time: 01-Mar-2019 09:32:04 GMT

Signature meaning: Approved

Approver: PPD

Approval Date & Time: 01-Mar-2019 09:52:34 GMT

Signature meaning: Approved

Approver: PPD

Approval Date & Time: 01-Mar-2019 13:30:37 GMT

Signature meaning: Approved

Approver: PPD

Approval Date & Time: 04-Mar-2019 21:02:20 GMT

Signature meaning: Approved
